10. STATISTICAL PLAN

This is a Phase 2, multicenter, randomized, single-blind, controlled trial in pediatric subjects undergoing hepatic, renal, soft tissue, spinal, or vascular surgery. Subjects will be recruited from up to 25 sites in the US. Subjects who qualify for entry into the study will be randomly assigned in a 2:1 ratio to receive either Raplixa plus gelatin sponge (R+G) or gelatin sponge alone (G). The objective of this study is to evaluate the safety and efficacy of Raplixa plus gelatin sponge, as compared to gelatin sponge alone, for achieving hemostasis in pediatric subjects undergoing hepatic, renal, soft tissue, spinal, or vascular surgery.

A separate Statistical Analysis Plan (SAP) document will provide more detailed specifications for data analysis and presentation.

10.1. SAMPLE SIZE

The sample size estimation is based on data from the completed Phase 3 trial (FC-004). Assuming the proportion of subjects achieving hemostasis within 4 minutes in R+G and G are 87% and 60% respectively, approximately 87 pediatric subjects (58 in R+G, 29 in G) will provide approximately 80% power to detect this difference at the one-sided significance level of 0.025 (equivalently, 2-sided significance level of 0.05) based on a chi-square test for 2 proportions.

10.2. RANDOMIZATION

Subjects will be randomized in a 2:1 ratio to the treatment groups R+G and G alone. Sealed, blinded envelopes will be provided by an external statistician, who also holds the randomization lists during the study. Only after the surgeon has identified an appropriate TBS, in the operating room, and notified the study coordinator that the site has been identified and he/she is ready for the treatment designation, will the Investigator/designee open a randomization envelope and record the time of randomization. If a randomization envelope has been opened and the subject does not receive the assigned study drug, this envelope may not be used for another subject.

10.3. GENERAL STATISTICAL CONSIDERATIONS AND DEFINITIONS

10.3.1. General Statistical Methods

All study-collected data will be summarized by treatment group using descriptive statistics, graphs, and/or raw data listings. Descriptive statistics for continuous variables will include number of subjects (n), mean, standard deviation (SD), median, quartiles (Q1 and Q3), minimum (min) and maximum (max) values. Analysis of categorical variables will include frequency and percentage. For time-to-event endpoints such as TTH, the Kaplan-Meier method will be used to estimate the survival distribution for each treatment group.

10.3.2. Analysis Populations

Two subject populations will be used for data analyses and/or presentations.

10.3.2.1. Intent-to-Treat (ITT) Population

The ITT population consists of all randomized subjects. This population will be the primary population for the efficacy analyses.

10.3.2.2. Safety Population

The safety population consists of all subjects who are exposed to any amount of study drug. Treatment classification will be based on the actual treatment received. This will be the primary population for the safety analyses.

10.3.3. Analysis Windows and Baseline

The observational period for the study includes Visit 1 (screening/baseline from Day -30 to Day 1), to Visit 5 (Day 30 ± 7 days, End of Study). An additional unscheduled observational period between Days 30 and 90 will be used to collect safety data from routine follow-up visits (not scheduled for the purpose of the study), if any such data were to be captured. Any event occurring after the defined observational period, even if collected on the eCRF, will not be included in the planned statistical analysis. However, all data, including that reported after the defined observational period, will be included in the subject data listings.

Unless otherwise specified, for evaluations that are collected at multiple occasions prior to initiation of study drug, the latest evaluation will be considered the "Baseline" evaluation for analysis.

10.3.4. Missing Data Handling

Unless otherwise specified, missing data will not be imputed and will be excluded from the associated analysis.

10.4. STATISTICAL ANALYSES

Summaries by treatment group will represent subject data across study sites. Descriptive statistics, graphs, and subject data listings will be used to summarize the data collected. For continuous variables, descriptive statistics will include the number of subjects reflected in the calculation (n), mean, standard deviation (SD), median, quartiles (Q1 and Q3), minimum (min), and maximum (max). Frequencies and percentages will be displayed for categorical data. Subject data listings will be presented by study sites, treatment group, surgery type, age cohort and subject number.

Unless otherwise specified, the primary population for efficacy analyses will be the ITT population; confirmatory analyses for efficacy will be performed using the safety population. All safety analyses will be performed using the safety population.

10.4.1. Demographic and Baseline Characteristics

Demographic variables will include age (continuous and by age cohort), sex, race, height, and weight. Baseline disease characteristics will include reason for surgery and related co-morbidities.

Subject demographics and baseline characteristics will be summarized by treatment group using the evaluable and safety populations.

10.4.2. Prior and Concomitant Medications

Summaries of each prior (pre-baseline) medication and concomitant (baseline or later) medication will be provided by treatment. Medications will be coded using the WHO Drug Dictionary. Subjects will be counted only once within each period by medication.

10.4.3. Safety Analysis

Overall safety, as determined by the incidence, severity and relationship of adverse events (AEs), clinical laboratory abnormalities, estimated rates of immunogenicity (monitoring for anti-thrombin antibodies and additional monitoring for anti-fibrinogen antibodies will be limited to subjects found positive for anti-thrombin antibodies and subjects with unexplained bleeding or clinical suspicion of bleeding related to antibody formation) and post-surgery bleeding complications.

10.4.3.1. Adverse Events

Adverse events (AE) will be coded using the Medical Dictionary for Regulatory Activities (MedDRA) dictionary. An AE (classified as preferred term) occurring during the study will be counted as a treatment emergent AE (TEAE) when it is not present at baseline or present at baseline but increased in severity after the initiation of study drug.

Summaries of the number and percentage of subjects with at least one SAE, MDR reportable events (malfunction, serious injury, or death), or MDV incident, and the number and percentage of subjects with at least one Grade 3, 4, or 5 AE, classified by MedDRA preferred term and system organ class, will be provided.

Adverse events of special interest as listed below will be summarized by treatment group. Details of the AEs of special interest are in Section 8.6:

- Surgical site-related events.
- Thromboembolic events.
- Re-bleeding at the bleeding sites.
- Gas embolism events.
- Blood borne pathogenic diseases suggestive of pathogen transmission from Raplixa.

Listings will be presented for subjects with SAEs/AEs leading to a treatment discontinuation or death.

The estimated rate of immunogenicity will be reported for both treatment arms. No immunogenicity data will be collected for, or reported on, children less than 6 months of age.

10.4.3.2. *Laboratory Tests*

Laboratory values will be summarized by treatment group, including changes and percentages of changes from baseline at each time point. Shift tables summarizing the counts and percentages of subjects who were normal at baseline, but became abnormal subsequently will be provided.

10.4.3.3. *Vital Signs*

Change and percent change from baseline in vital signs will be summarized descriptively at each scheduled time point by treatment group.

10.4.4. *Efficacy Analysis*

10.4.4.1. *Primary Efficacy Endpoints*

The primary efficacy endpoint is:

- Proportion of subjects who reach hemostasis at the first identified TBS within 4 minutes of study drug application.

If a subject achieves hemostasis at any point within 4 minutes of study drug application, they will be considered a “success”. All other subjects will be considered a “failure”.

The primary endpoint will be analyzed with the ITT population. Comparison of the overall response between treatment arms will be made using logistic regression. This will include the estimation of the overall response rates, with 95% confidence intervals, for each treatment arm. Surgical type may also be included in the analysis model as a potential covariate in order further assess the endpoint.

Additional details of this analysis will be described in the SAP.

10.4.4.2. *Secondary Efficacy Endpoints*

The secondary efficacy endpoints are:

- Restricted mean TTH (during the 5-minute TTH assessment period)
- Through Visit 5, EOS visit:
 - Use of alternative hemostatic agents on the TBS.
 - Volume of transfused blood (whole blood, fresh frozen plasma (FFP), cryoprecipitate, platelets, or packed red blood cell (PRBC).
 - Incidence of re-operation for bleeding at the TBS.

The analysis of these variables will be described in the SAP.

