4.3. EXCLUSION CRITERIA

Exclusion Criteria

Subjects will be excluded from the study if any of the following exclusion criteria apply prior to enrollment:

1. Gestational age of < 36 weeks at birth (for infants less than 6 months).
2. Subject has any clinically-significant congenital coagulation disorder (e.g., hemophilia A or B) that may interfere with the assessment of efficacy or pose a safety risk to the subject according to the Investigator.

3. Subject has baseline abnormalities of international normalized ratio (INR) > 2.5 or activated partial thromboplastin time (aPTT) > 100 seconds during screening that are not explained by current drug treatment (e.g., warfarin, heparin) or chronic disease state necessitating surgery (e.g., end stage liver disease).
4. Subject has aspartate aminotransferase (ASAT/AST) and alanine aminotransferase (ALAT/ALT) > 3 times the upper limit of reference range during screening, except for subjects undergoing liver resection surgery or with a diagnosis of liver disease where there is no upper limit for these analytes due to the nature of their disease.
5. Subject is unwilling to receive blood products or products derived from human blood
6. Subject has platelets < 100 x10⁹ PLT/L during screening, unless due to chronic disease state, e.g., liver disease/failure, necessitating surgery.
7. Subject has known antibodies or hypersensitivity to Raplixa or any of its components, other thrombin preparations, or coagulation factors.
8. Subject has known allergy to porcine gelatin.
9. Subject has medical, social, or psychosocial factors that, in the opinion of the Investigator, could impact subject safety or compliance with study procedures.
10. Subject is; 1) currently participating in another clinical study or 2) has participated in another clinical study within 30 days of screening or 3) plans to participate in a clinical study prior to completion of the 30-day follow-up period.

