8.1.1.1. AE Severity

The severity of an AE and the relationship to study drug will be assessed by the investigator. The investigator should ensure that any subject experiencing an AE receives appropriate medical support until the event resolves.

AE severity will be assessed according to the grading scale in the Common Terminology Criteria for Adverse Events (CTCAE) version 4.0:

Grade 1: Mild; asymptomatic or mild symptoms; clinical or diagnostic observations only; intervention not indicated.

Grade 2: Moderate; minimal, local or noninvasive intervention indicated; limiting age-appropriate instrumental Activities of Daily Living (ADL)*.

Grade 3: Severe or medically significant but not immediately life-threatening; hospitalization or prolongation of hospitalization indicated; disabling; limiting self-care ADL**.

Grade 4: Life-threatening consequences; urgent intervention indicated.

Grade 5: Death related to AE.

*Instrumental ADL refer to preparing meals, shopping for groceries or clothes, using the telephone, managing money, etc.

**Self-care ADL refer to bathing, dressing and undressing, feeding self, using the toilet, taking medications, and not bedridden.

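### The laboratory shift tables count only normal-to-abnormal changes, so for each analyte they cannot count worsening in subjects who enter with an abnormal value

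*Combined protocol and SAP*

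**What the plan says.** Section 10.4.3.2 (Laboratory Tests) describes two displays. The first is numerical: "Laboratory values will be summarized by treatment group, including changes and percentages of changes from baseline at each time point". It is not restricted by baseline status. The second is categorical: "Shift tables summarizing the counts and percentages of subjects who were normal at baseline, but became abnormal subsequently will be provided". The supplied text describes no other laboratory shift table.

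Section 4.3 lets subjects enter with abnormal values:

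- **AST/ALT (criterion 4).** Values "> 3 times the upper limit of reference range during screening" lead to exclusion, but the criterion carries an exemption for hepatic cases, worded as follows: "except for subjects undergoing liver resection surgery or with a diagnosis of liver disease where there is no upper limit for these analytes".
- **INR/aPTT (criterion 3).** INR above 2.5 or aPTT above 100 seconds excludes only for abnormalities "that are not explained by current drug treatment (e.g., warfarin, heparin) or chronic disease state necessitating surgery (e.g., end stage liver disease").
- **Platelets (criterion 6).** A count below 100 x10⁹/L excludes "unless due to chronic disease state, e.g., liver disease/failure, necessitating surgery".

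Section 3.3 makes clinical laboratory abnormalities part of the safety endpoint. Section 8.1.1.1 states: "AE severity will be assessed according to the grading scale in the Common Terminology Criteria for Adverse Events (CTCAE) version 4.0".

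**The concern.** The table is built for a population that starts normal, while the eligibility rules deliberately include subjects who do not. Worsening from an already abnormal value has no cell. For illustration, a fall in platelets from 80 to 20 x10⁹/L or a rise in INR from 2.6 to 5 would not be counted. A value that moves from just inside to just outside its range would be counted, and on equal terms with a move from normal to a critical value.

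The affected analytes matter here. The product is thrombin plus fibrinogen, and apart from antibody testing the coagulation panel and platelets are the scheduled systemic measures of haemostasis. Infants under 6 months have no immunogenicity sample, so the coagulation panel is their only scheduled Day 30 laboratory test (Table 3). With planned arms of 58 and 29, a few uncounted subjects can change how the by-arm comparison looks. A report could show similar shift counts in the two arms while subjects outside the count had clearly worsened.

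**Working it through.** The plan gives no figure for laboratory shifts, so the main check sets the sections side by side.

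**1. Who can enter with an abnormal value (Section 4.3).**

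| Analyte | Abnormal at baseline and eligible |
|---|---|
| AST/ALT, liver resection or liver disease | any elevation |
| AST/ALT, other subjects | above the upper limit, up to 3 times it |
| INR, aPTT | above 2.5 or 100 s if explained by drug treatment or chronic disease |
| Platelets | below 100 x10⁹/L if due to chronic disease |

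Hepatic surgery is one of the five enrolled indications (Section 4), so the first row is not a remote case.

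**2. What the shift table can count (Section 10.4.3.2).** Counting needs a normal baseline and a later abnormal value. For any row above, the first condition fails for that analyte, so the subject's chance of being counted for it is zero whatever happens later. The same subject can still be counted for analytes that were normal at baseline.

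**3. Comparison with the adverse event rule.** Section 10.4.3.1 treats an event as emergent also when a condition already present at baseline becomes more severe. The laboratory table does not follow that principle.

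**4. What the other displays give.**

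- *Values and changes:* Sections 10.3.1 and 10.4 specify n, mean, SD, median, quartiles, minimum and maximum. An extreme value may show as the arm's minimum or maximum. How many subjects worsened, and from what baseline, does not.
- *Listings:* they hold every value but no count by arm.
- *Adverse events:* an abnormal laboratory finding can be an AE (Section 8.1.1) and would then be graded. Standard post-operative occurrences, however, are reported only if judged unfavourable (Section 8.1.6), and investigators are not blinded (Section 5.6.1).

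**5. Planned size, for context.** Section 10.1 gives 87 subjects (58 and 29) for about 80% power at 87% versus 60%, two-sided 0.05. With a pooled-variance chi-square test and no continuity correction:

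- pooled proportion = (58 × 0.87 + 29 × 0.60) / 87 = 0.78
- SE under the null = √[0.78 × 0.22 × (1/58 + 1/29)] = 0.0942
- SE under the alternative = √[0.87 × 0.13/58 + 0.60 × 0.40/29] = 0.1011
- z = (0.27 − 1.96 × 0.0942) / 0.1011 = 0.844, so power is 80.07%

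The stated figure reproduces. The laboratory point does not depend on it, beyond using 87, 58 and 29 as group sizes.

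**6. Possible size of the gap.** Let q be the share abnormal at baseline on one analyte. The documents do not give q; the range 0.10 to 0.40 is an assumption. Uncountable subjects = q × n.

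| | q = 0.10 | q = 0.40 |
|---|---|---|
| All (87) | 8.7 | 34.8 |
| R+G (58) | 5.8 | 23.2 |
| G (29) | 2.9 | 11.6 |

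The table's denominator is not stated either. If it were all treated subjects, the reported percentage would be (1 − q) times the percentage among those normal at baseline, that is 0.9 to 0.6 times. With q balanced between arms, this would shrink both percentages alike and leave their ratio unchanged.

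**The case against.** The strongest reply is that little is lost. No subject is dropped from the numerical summaries, and those include minimum and maximum, not means alone. Listings are organised by site, arm, surgery type and age cohort, so hepatic subjects can be found. Serious worsening should reach the AE tables, where existing conditions that become more severe count and Grade 3 to 5 events are tabulated. Haematology and chemistry have one scheduled post-treatment draw, so a worst post-baseline value adds little there. The display is descriptive, no decision rule rests on it, and Section 10 defers detail to a separate SAP that is not in the supplied text and could add a fuller table.

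Most of this stands, and it rules out several stronger readings that a reader might infer:

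- *That subjects with an abnormal baseline vanish from the shift tables.* The loss is per analyte; a liver-disease subject with normal enzymes is not lost at all.
- *That their worsening is invisible.* It can appear in the extremes, the listings and the AE tables.
- *That the plan sets normal-to-abnormal as its threshold for a safety signal.* Section 10.4.3.2 describes a table and sets no threshold, and the data monitoring committee's review in Section 3.1 is not tied to it.
- *That no fuller table will ever be produced.* The supplied text cannot establish this.

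What the reply does not supply is a by-arm count of subjects whose laboratory values worsened from an abnormal baseline. The AE route depends on unblinded judgement. A SAP that keeps to the protocol's explicit shift definition would carry the gap forward.

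**Conclusion.** The point holds as a limited one. Section 10.4.3.2 states a rule, and read with Section 4.3 that rule gives an incomplete by-arm count for a named safety endpoint, one analyte at a time and without severity. The textual finding needs no assumption. Its size does: about 9 to 35 of 87 subjects uncountable for an analyte if 10% to 40% are abnormal on it at baseline, a range the documents neither support nor contradict. The consequence is confined to a descriptive safety display. The primary analysis, its power and the collected data are unaffected. The change is worth making because it is cheap and the affected analytes are relevant to this product.

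**What to change.** In Section 10.4.3.2 and the SAP, replace the normal-to-abnormal table with a shift table for each analyte by arm: baseline category (low, normal, high, or CTCAE v4.0 grade where one exists) against worst post-baseline category, including subjects abnormal at baseline. Add a line with the number and percent who worsen by at least one category or grade, and state the denominator as subjects with both a baseline and a post-baseline value. Use grades where they exist, because a high value that rises further stays in the same low/normal/high category.

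The cost is SAP wording and table programming. No new data are needed, and CTCAE v4.0 is already the protocol's AE severity scale. The downside is larger tables, with some sparse cells in arms of this size.

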3. TRIAL DESIGN

3.1. TYPE/DESIGN OF TRIAL

This is a Phase 2, multicenter, randomized, single-blind, controlled trial comparing the efficacy and safety of Raplixa in combination with an absorbable gelatin sponge to gelatin sponge alone, in pediatric subjects undergoing hepatic, renal, soft tissue, spinal, or vascular surgery. The study will enroll approximately 87 subjects at up to 25 sites in the US.

Informed consent will be obtained from parents/guardians for each subject before any protocol-related assessments or procedures are conducted. Subjects 7 years and older, or of an appropriate age as defined by local regulations, may be required to provide assent to participate in the study.

Eligible subjects will be randomized in a 2:1 ratio to receive treatment with Raplixa in combination with an absorbable gelatin sponge (active group; R+G) or gelatin sponge alone (control group; G) when an appropriate target bleeding site (TBS) is identified. Subjects who are not treated with study drug will be withdrawn from the study and may be replaced.

Reasons for not receiving study drug include, but are not limited to; lack of an appropriate TBS for time to hemostasis (TTH) evaluation, severe bleeding, or a change in surgical procedure that renders the subject ineligible, after the subject has been randomized.

Subjects will be enrolled across 4 different age groups, with the 2 oldest age groups enrolled simultaneously: 1) 11 years of age to less than 18 years of age; 2) 2 years of age to less than 11 years of age; 3) 6 months of age to less than 2 years of age; or 4) ≥ 36 weeks gestational age at birth to less than 6 months of age. Following completion of Visit 5, Day 30, for 6 subjects treated with Raplixa plus gelatin sponge within 1 of the 2 oldest age groups, the Independent Data Monitoring Committee (IDMC) will review all available safety data and verify that the observed safety profile supports continued subject enrollment. Study enrollment will not be stopped during the IDMC review. After the IDMC review, this body will notify the study team if the safety assessment shows that there is a favorable benefit-to-risk outcome to continue enrollment in the two older cohorts, and whether it is acceptable to initiate sequential enrollment in the two lower age cohorts.

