6.2.2. Visit 2: Surgery, Randomization, and Treatment

Pre-Operative

Pre-operative procedures and assessments include:

1. Review eligibility.
2. Review and record concomitant medications.
3. Assess and record AEs.
4. Measure and record vital signs.
5. Pregnancy Test - only for females of childbearing potential (must document in the subject's source document the reason for the inability to become pregnant).
6. Assess and record changes to baseline health status (changes in health or medical conditions since the screening visit).

Surgery, Randomization and Treatment

The surgery will be carried out according to the local standardized surgical practices; these are not covered within this protocol. Subjects will be randomized after the start of surgery to reduce potential bias.

1. Confirm subject eligibility:
 - a. Subject has not received any whole blood, fresh frozen plasma (FFP), cryoprecipitate, or platelets between screening and study drug. Packed red blood cell (PRBC) transfusions are allowed.
 - b. There is a TBS with mild or moderate bleeding/oozing. The bleeding intensity will be assessed by the Investigator according to the following description:

Mild: Oozing and/or capillary leakage

Moderate: Gradual and steady flow
 - c. There are no significant intra-operative complications other than bleeding which, in the opinion of the Investigator, may interfere with assessment of efficacy or safety.
 - d. The TBS surface area is $\leq 100 \text{ cm}^2$.

NOTE: If subjects do not meet these intra-operative criteria, they will be deemed screen failures and their demographic data and specific reason for ineligibility will be captured on appropriate eCRF pages.

2. Randomize subject to treatment group when an eligible TBS is identified. Record the time the subject was randomized.
3. Subject treatment, based on randomization (TTH clock starts as soon as the application of the assigned treatment begins).

- a. Raplixa + Gelatin Sponge Group: Rapidly apply Raplixa using one of the following three methods:
 - i. Sprinkle a thin layer of Raplixa directly from the vial onto the TBS followed by application of a gelatin sponge (wet or dry).
 - ii. Spray a thin layer of Raplixa onto the TBS using the RaplixaSpray device followed by application of a gelatin sponge (wet or dry).
 - iii. Apply Raplixa onto a moistened absorbable gelatin sponge that is then applied to the TBS.

Light manual pressure using sterile gauze should follow for all three application methods.

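### The primary logistic regression does not prespecify adjustment for bleeding intensity, which is graded before randomization: a cheap improvement to a valid test

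*Combined protocol and SAP*

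**What the plan says.** Section 10.4.4.1 applies to the intent-to-treat (ITT) population: "Comparison of the overall response between treatment arms will be made using logistic regression". It promises a response rate with a 95% confidence interval for each arm, then adds "Surgical type may also be included in the analysis model as a potential covariate in order further assess the endpoint". Further detail is deferred to a separate SAP, and the document supplied contains no such text.

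Section 6.2.2 sets the order of events in the operating room. Step 1b covers the target bleeding site (TBS): "The bleeding intensity will be assessed by the Investigator according to the following description". The two grades are mild (oozing or capillary leakage) and moderate (a gradual, steady flow). Randomization is step 2. Sections 3.4.1, 5.6.2 and 10.2 agree that the envelope is opened only after the site has been identified. Section 3.4.1 links the envelope to the type of surgery. No section links it to bleeding intensity.

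Section 10.1 sizes the trial without covariates. It takes success rates of 87% on R+G and 60% on G from the Phase 3 trial and states the result: "approximately 87 pediatric subjects (58 in R+G, 29 in G) will provide approximately 80% power". The level and the test behind that figure are set out there too: "one-sided significance level of 0.025 (equivalently, 2-sided significance level of 0.05) based on a chi-square test for 2 proportions".

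**The concern.** The grade is fixed before allocation, so treatment cannot influence it, and it is clinically plausible that a steady flow is harder to stop within 4 minutes than an ooze. A baseline variable of this kind is a natural covariate for the primary model.

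With only 29 controls, the arms can differ noticeably in their share of moderate bleeds by chance. An unadjusted comparison carries that difference into the estimate. The baseline disease characteristics named in section 10.4.1 do not include intensity, so an imbalance might not appear in the planned summaries either.

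Timing matters because section 5.6.1 leaves investigators, site personnel and the Sponsor's study team unblinded. A covariate chosen late by people who know the allocation would be open to challenge. One named in advance would not.

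**Working it through.** **Inputs from the protocol.** Section 10.1: 87% and 60% success; 58 and 29 subjects; two-sided 5% level; chi-square test. Section 10.2: "Subjects will be randomized in a 2:1 ratio to the treatment groups R+G and G alone". **Assumed, because the documents give no value:** the moderate share (30% or 50%) and the OR for success, mild against moderate.

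**1. The plan's own figure.** Pooled rate = (58 × 0.87 + 29 × 0.60)/87 = 0.78.
- Null SE = √[0.78 × 0.22 × (1/58 + 1/29)] = 0.0942.
- Alternative SE = √[0.87 × 0.13/58 + 0.60 × 0.40/29] = 0.1011.
- Power = Φ[(0.27 − 1.96 × 0.0942)/0.1011] = Φ(0.844) = 80.1%.

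The stated figure reproduces. Exact enumeration gives 81.3% for the Pearson chi-square and 80.8% for unadjusted logistic regression, by Wald or likelihood ratio.

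**2. Effect of adjustment on power.** Simulated logistic regression with and without the binary grade, marginal rates held at 87% and 60%, 20,000 trials per cell (Monte Carlo SE about 0.3 point). Likelihood-ratio power in %, unadjusted → adjusted:

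| Assumed OR | 30% moderate | 50% moderate |
|---|---|---|
| 1 | 81.4 → 80.9 | 81.2 → 80.5 |
| 2 | 80.7 → 80.4 | 80.7 → 80.7 |
| 3 | 80.7 → 82.0 | 81.0 → 81.9 |
| 5 | 80.9 → 84.1 | 81.2 → 84.0 |

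A repeat simulation gave +2 to +3 points at OR 4 and +3 to +4 at OR 5. The likelihood-ratio type I error was 5.2% to 5.7% with or without the term.

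**3. How often the arms differ.** With half the bleeds moderate, the SD of the difference in moderate share = √[0.25 × (1/58 + 1/29)] = 0.114. A gap of at least 10 points then has probability 2[1 − Φ(0.10/0.114)], about 38%. A gap of at least 20 points has probability about 8%.

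**4. What a gap does to the estimate.** Let o be the odds of success in a moderate bleed. Solving ½[OR·o/(1 + OR·o) + o/(1 + o)] = p gives:
- OR 2: control (p = 0.60) 68.2% mild, 51.8% moderate, gap 16.5 points; R+G (p = 0.87) 90.8% and 83.2%, gap 7.6.
- OR 4: control 75.9% and 44.1%, gap 31.8; R+G 94.1% and 79.9%, gap 14.2.

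Hold the overall mix at 50% and let the control arm have d more moderate bleeds, as a proportion, than R+G. Control then lies 2d/3 above the overall share and R+G lies d/3 below it, since 29 × 2d/3 = 58 × d/3. The unadjusted difference shifts by d × (⅔ × control gap + ⅓ × R+G gap).
- d = 0.10: 0.10 × (10.97 + 2.55) = 1.4 points at OR 2; 0.10 × (21.2 + 4.7) = 2.6 points at OR 4.
- d = 0.20: 2.7 and 5.2 points.

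**5. Room for the term.** Expected failures = 58 × 0.13 + 29 × 0.40 = 19.1, enough for one extra parameter.

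**The case against.** A reader might infer that the planned test gives up power. The documents do not support that as a fact. They give no prognostic effect, and both grades lie within a single eligibility band. The trial was sized on an unadjusted test, and that test delivers what section 10.1 states. At OR 2 the gain is nil. A gain of 5 points appears only at an assumed OR of 8 (80.0% to 85.0%, half moderate). Chance imbalance under randomization is not bias, and the confidence interval already allows for it. All of this stands.

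A reader might also say that the plan ignores intensity. That is too firm, because the covariate list may be completed in a SAP that is not in the document. What can be said is that the protocol does not prespecify the term.

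Two practical objections also stand. Section 6.2.2 requires the grade for eligibility but does not expressly require it on the eCRF, and section 9 allows 48 hours for eCRF entry, by which time the investigator knows the allocation. Further, the ITT population includes subjects randomized but left untreated, for example for want of a suitable site or because of severe bleeding (section 3.1: "Subjects who are not treated with study drug will be withdrawn from the study and may be replaced"). Some may have no applicable grade, and section 10.3.4 would exclude them.

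Surgical type is the better-documented gap, since the envelopes follow it and the model only may include it. It has five categories against about 19 expected failures. That does not remove the case for intensity, but the two should be settled together.

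**Conclusion.** The point holds as a low-cost improvement. The protocol does not commit to adjusting for a grade that precedes allocation, is not balanced by design and plausibly predicts 4-minute hemostasis. The expected power change runs from about -1 to +4 points over OR 1 to 5. The protection against imbalance is worth roughly 1.4 to 2.6 points of the 27-point difference per 10 points of imbalance (OR 2 to 4, half moderate). These sizes rest on an assumed split and prognostic strength.

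Three stronger conclusions should be avoided:
- The trial is not underpowered against its own target, and its primary test is not invalid.
- Applying the control-arm gap to both arms would put the shift at 1.6 to 3.2 points per 10, which overstates it because the gap at 87% is less than half as large.
- It cannot be taken for granted that the grade is already captured for every randomized subject.

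**What to change.** In section 10.4.4.1 or the SAP, before analysis:
- Name pre-randomization bleeding intensity (mild or moderate) as a fixed covariate in the primary logistic regression, and test treatment by likelihood ratio.
- Report the response rate per arm and their difference, with 95% confidence intervals, by averaging model predictions over all randomized subjects. This keeps the per-arm rates that the section promises.
- State that the grade is recorded on the eCRF as assessed before the envelope was opened.
- Keep ITT subjects with a missing or inapplicable grade in the model by a simple rule applied without regard to arm, such as assigning the more common category, so that section 10.3.4 does not drop them.
- In the same place, replace the optional wording on surgical type with a decision.

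The cost is a few sentences, confirmation that the grade is captured, and under about 1 point of power if intensity proves not to be prognostic.
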